APPENDIX 9: Randomisation, concealment and code-break

has suffered an unexpected serious adverse event (e.g. anaphylaxis; admission to hospital with life threatening illness (e.g. septicaemia; meningitis; severe pneumonia requiring ITU admission; death)).

The Code-break will only be released to the investigative team once written confirmation has been received that primary outcome data analysis is complete. The UH Bristol Pharmacy will also record a list of all participants and their treatment allocation and file this in the pharmacy trial file and provide a copy to the Trial Manager at the end of the trial. Formal SOPs will be developed to describe each of these procedures in detail.

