Post Day 8 (Trial Nurse/Administrator telephone call): Parents whose children are still experiencing ear pain at after 7 days following the day of randomisation will continue to be telephoned twice weekly in order to identify the date on which the child's parent-reported ear pain had resolved for two consecutive days, without analgesic medication. We estimate that 10% of children will still be symptomatic at this point (Day 8)¹⁷. Parents will be asked to score their child's ear pain (on average over the preceding 24 hours) and to report any oral antibiotic or analgesic consumption.

Month 3 (primary care notes review and postal/ telephone questionnaire) will include: primary care notes review for primary and secondary care attendances, and Serious Adverse Events and a postal/telephone questionnaire to collect CHU-9D and OMQ-14, following which the study team will send the parent a £5 voucher.

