11. ASSESSMENT OF EFFECTIVENESS

Primary outcome

1. Any antibiotic consumed by Day 8 (measured using daily Symptom and Recovery Questionnaire with telephone support calls during week 1), where Day 1 is the day of randomisation;

Secondary outcomes

[Key secondary outcome]

2. Ear pain over first 24-36 hours post randomisation using the parent completed, validated numerical rating scale successfully used in our previous trial⁶ (Symptom and Recovery Questionnaire with telephone support call in first three days).

[Other secondary outcomes]

- 3. Time taken before antibiotics started (Symptom and Recovery Questionnaire with telephone support calls during week 1);
- Daily symptom severity (until illness resolution i.e. child free of ear pain without need for rescue analgesia for two consecutive days, expected by 8 days for most children¹⁷) including episodes of distress/crying, disturbed sleep, interference with normal activity, appetite, fever and hearing problems (Symptom and Recovery Questionnaire, supported by telephone calls);
- 5. Child completed Faces Pain Scale-Revised (FPS-R [Hicks et al 2001], for children aged ≥5 years) (Symptom and Recovery Questionnaire);
- 6. Adverse events (Symptom and Recovery Questionnaire, supported by telephone calls);
- 7. Ear drop and rescue analgesia consumption (Symptom and Recovery Questionnaire, supported by telephone calls);
- Parent satisfaction with, and opinion of, treatment allocation and future intention to use drops (with/without prior GP consultation if drops were to become available over-the-counter) after 7 days (Symptom and Recovery Questionnaire, with telephone support call at one week);
- Preference based quality of child life measured (baseline, 24-36 hours, 7 days and 3 months post randomisation) using CHU-9D¹⁸ for children age ≥5 years (CRF, Symptom and Recovery Questionnaire supported by telephone calls, and postal/online questionnaire at 3 months)
- 10. NHS costs up to 7 days after randomisation (Symptom and Recovery Questionnaire, supported by telephone call at one week) and contacts to 3 months (primary care medical notes review);

- 11. Child's school/nursery absences, parent lost productivity and other expenses up to 7 days after randomisation (Symptom and Recovery Questionnaire, supported by telephone calls)
- 12. Child's quality of life (OMQ-14,¹⁹ for children aged 2 years and older) at baseline and 3 months after randomisation (CRF and postal/online questionnaire at 3 months).

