The key secondary analysis will analyse the difference in pain scores, between the active and placebo groups, 24-36 hours after administration of drops. This information will be collected using the Symptom and Recovery Questionnaire by asking the parents to score their child's ear pain over the past 24 hours on the evening of Day 2. The analysis–will be conducted using linear regression, adjusting for baseline pain score (collected prior to randomisation) and centre. This will be followed by a linear regression model where all other principles described for the primary analysis above will be applied, including the potential mediating effect of antibiotic use and other analgesics on how this might affect the interpretation of the results. Other secondary analyses will use the appropriate regression method, and, as these will be exploratory in nature, the p-value will be presented but will interpreted with due caution. The analysis will be conducted using the statistical package STATA. The trial statistician and senior statistician will be blinded to the different arms of the trial for the main analysis.

At the pre-funding stage, two reviewers identified that the use of antibiotics and analgesics could influence the effect of the ear drops on pain. Although evidence suggests the effects of antibiotics are modest [[name] BMJ 2001], on consideration we agree and will not adjust for post-randomisation health care variables such as analgesics and antibiotics in our main models or when reporting our main results. However as part of secondary sensitivity analyses, we will look at the mediating effect of analgesics and antibiotics to help interpret and contextualise our main findings, with the potential for confounding kept in mind.

We will measure selection bias, model the effects of any selection bias, and provide descriptive data regarding the presentation, management and outcome of children with AOM who are not recruited into a trial. We found evidence that fewer than 44% of eligible children were recruited into AOM trials [Bains 2001] and that the most likely reason for not recruiting was severity. To test this within CEDAR and to inform the assessment of generalisability, we will compare the global illness severity scores, made by parents and clinicians at baseline, across the RCT and OCS.

A full Statistical Analysis Plan will be developed and reviewed by the Trial Steering Committee.

Health economic analysis

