Once participant eligibility is confirmed and written informed consent obtained, the parent will be given the next available sequentially numbered Patient Pack. If the Medicine ID number indicates that the child has been allocated to one of the medicine arms, the clinician will retrieve the single bottle of ear drops for which the Medicine ID number corresponds to that provided in the Patient Pack. For participants in the treatment arms, Quality Assurance will be achieved by asking a third party (another member of the practice team) to verify that the Medicine ID number in the Patient Pack has been correctly matched to the Medicine ID number on the Medicine Pack containing the bottle. For participants in the control arm, no matching will be necessary.

The patient ID number will be different to the Medicine ID number to enable flexibility in the numbers recruited at each Centre, allowing medicine packs to be combined with patient packs allowing for temporary fluctuations in recruitment rates between Centres.

The primary research question ("do drops reduce antibiotic consumption") is best addressed using a pragmatic, open design since knowledge of treatment allocation (as well as the treatment itself) is known to be an important driver of antibiotic consumption [[name] BMJ 2001] and will provide estimates of 'real world' pragmatic effect sizes. However, to investigate effects on pain (subjective outcome and secondary research question) requires a blinded design. One of the reasons to have a 1:1:1 randomisation strategy in the three arms is that the trial statistician will be blind to patient allocation.

The UH Bristol Pharmacy will hold the randomisation schedule and a log of which Medicine Pack was put into which Patient Pack (hereafter referred to as the Code-break) and provide a 24 hour emergency unblinding service. During working hours (Monday to Friday, 9am to 5pm), concerned clinicians should contact the UH Bristol Pharmacy Clinical Trials Unit on [name]. Out-of-hours, the Trust on-call Emergency Duty Pharmacist is available via the Trust switchboard [name]. Each parent will be given a Trial Participation Card with details of who the child's Responsible Clinician should contact in the event of an emergency. The Trial Manager and Centre Co-ordinators will also hold these cards.

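### The code-break may be released once the primary outcome analysis is complete, without requiring that the blinded active-versus-placebo pain analysis or the 3-month follow-up be finished

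*Protocol*

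**What the plan says.** Appendix 9 of the protocol gives the release rule: "The Code-break will only be released to the investigative team once written confirmation has been received that primary outcome data analysis is complete". It sets a separate point for the pharmacy's list of participants and allocations, which is to "provide a copy to the Trial Manager at the end of the trial". Release of the code-break is therefore not tied to the end of the trial.

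Section 11 defines the primary outcome as "Any antibiotic consumed by Day 8 (measured using daily Symptom and Recovery Questionnaire with telephone support calls during week 1"), and section 12.5 compares it between active drops and no drops. Appendix 9 says that this question "is best addressed using a pragmatic, open design since knowledge of treatment allocation (as well as the treatment itself"), because both influence antibiotic use. It then says that "to investigate effects on pain (subjective outcome and secondary research question) requires a blinded design".

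Pain is the powered key secondary outcome. Section 12.5 states: "The key secondary analysis will analyse the difference in pain scores, between the active and placebo groups, 24-36 hours after administration of drops". The same section says that the two statisticians stay blinded to the arms for the main analysis, a term it does not define.

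Follow-up continues after Day 8. Section 10.2 lists for Month 3 "primary care notes review for primary and secondary care attendances, and Serious Adverse Events and a postal/telephone questionnaire to collect CHU-9D and OMQ-14". Section 9.21 has the study team send the questionnaire. The synopsis assigns the notes review to primary care site staff.

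**The concern.** The release condition protects the comparison that the protocol calls open and leaves out the one that it says must be blinded. Clinician and parent learn at pack opening whether the child has drops. What the code-break hides is active versus placebo, and the comparison that depends most on that is pain.

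If the code is released while pain is still being analysed, choices that depend on the data could be made with the arms known. This matters because the provisional recommendations (a) to (d) in section 4.3 all draw on the pain result or on how active and placebo drops compare.

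A lesser issue is that the condition can be met while the study team is still sending 3-month CHU-9D and OMQ-14 questionnaires to the last children recruited. Section 16 relies on OMQ-14 for parents' perception of hearing.

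**Working it through.** **1. What the release condition covers**

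| Item | Where | Named in the condition? |
|---|---|---|
| Antibiotics by Day 8, active vs no drops (primary) | Sections 11, 12.5 | Yes |
| Pain at 24-36 hours, active vs placebo (key secondary) | Sections 11, 12.1, 12.5 | No |
| 3-month questionnaire and notes review | Sections 9.21, 10.2 | No |
| Database lock | – | No |

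**2. Which pain analysis decisions are still open**

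- The first pain model in section 12.5 is fixed: linear regression on baseline pain and centre. Knowing the arms gives little room there.
- A second model follows the principles of the primary analysis: adjustment for marked baseline imbalance, and transformation of clearly non-normal outcomes. Both depend on the data.
- Mediation analyses for antibiotics and analgesics come after that.
- Appendix 7 leaves the pain summary as a mean, median or log mean according to the distribution.

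All of these could be decided after release under the rule as written. The documents give no basis for putting a number on the resulting bias.

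**3. What is not exposed**

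The pain score is recorded on the evening of Day 2, before Day 8. Release after the primary analysis cannot affect its collection.

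**4. Size of the 3-month overlap**

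Inputs:
- Day 8 is 7 days after randomisation (section 10.1).
- Three months is taken as 91 days (assumption).
- Recruitment lasts 24 months, or 730 days (section 6.8), with uniform accrual (assumption).
- The plan has 167 children per arm. Section 12.1 gives 133 / 0.8 = 166.25, rounded up to 167, and 3 × 167 = 501, which agrees with the stated total. Active plus placebo is 2 × 167 = 334.

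The window between the last child's Day 8 and 3-month point is 91 − 7 = 84 days. If the primary analysis is complete L days after that Day 8, the share of children not yet at three months is (84 − L) / 730:

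| L (assumed) | Share | Of 334 active and placebo children |
|---|---|---|
| 0 days | 84/730 = 11.5% | about 38 |
| 42 days | 42/730 = 5.8% | about 19 |
| 84 days or more | 0% | 0 |

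The first row is the ceiling under these assumptions, since data return, cleaning and analysis all take time. Accrual that speeds up late would raise the share, and recruitment longer than 24 months would lower it. The count covers children who have not reached three months. Questionnaires sent but not yet returned are not included, because the protocol gives no return time.

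Appendix 7 adds GP records as a source for the primary outcome, whereas the synopsis and section 11 name only the questionnaire and calls. If those records come from the 3-month notes review, the primary analysis could not finish before that review and the overlap largely disappears. The protocol does not settle this.

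**The case against.** **Statistician blinding.** The sentence in section 12.5 closes the paragraph that sets out the pain analysis, and the next paragraph, on the effect of the drops on pain, speaks of main models and main results. It is natural to read the main analysis as including pain. This has weight, but the term is undefined and the sentence covers only the two statisticians, while the code goes to the investigative team. The two places need to be aligned.

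**Pain as a primary outcome.** The health economics part of section 12.5 lists ear pain among the primary outcomes, and section 10.1 chooses the pain scale for the primary outcome. The release condition may have been meant to include pain. Formally, though, the synopsis and sections 5.4, 11 and 12.1 all make it secondary, so the condition as worded does not secure it.

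**Earliest release, not automatic release.** The rule says when the code may be released, not that it will be released then. This stands. A reader might infer that the pain comparison loses its blinding, or that all 334 children will be analysed unblinded. The protocol gives no order for the two analyses, and both can be run from the same Day 1-8 questionnaire, so neither inference is supported.

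**3-month follow-up.** A reader might apply 11.5% to all 501 children and count about 58, or suppose that unblinded investigators carry out the notes review. The no-drop children were never blinded, the review belongs to site staff, and parents complete the questionnaires without being told their allocation until after the trial. What remains is the study team's handling of questionnaires for outcomes that were not powered.

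**SAP and SOPs.** A full analysis plan and procedures for the code-break are promised and may tighten this. Nothing in the protocol says that they will change the release condition.

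**Conclusion.** The point holds as a gap in the release rule. Appendix 9 permits unblinding of the investigative team before the powered active-versus-placebo pain analysis is finished, although the same appendix says that pain needs a blinded design. Section 12.5 only partly closes the gap. The exposure is to the follow-on pain model, the choice of summary and the mediation analyses. The first pain model has fixed covariates, and the pain data are already collected.

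The 3-month part is secondary. At most about 11.5% of active and placebo children (about 38 of 334) would not have reached three months at release. That assumes uniform 24-month accrual and a primary analysis completed at the last child's Day 8. The figure falls, possibly to none, with realistic analysis time or if GP records from the 3-month review feed the primary outcome.

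The documents do not show that blinding will be lost, only that the rule allows it. This is a worthwhile and inexpensive correction, not a flaw that undermines the trial.

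**What to change.** 1. In Appendix 9, make release of the code-break conditional on all of the following: 3-month questionnaire and notes-review data entered; database locked; and both the primary and the key secondary pain analyses completed on coded arms and signed off. The pain analyses should include the follow-on model and the mediation analyses.
2. In section 12.5, state that the main analysis for which the statisticians are blinded includes the pain analysis.
3. Leave the emergency unblinding procedure as it is.

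The cost is a change to one sentence in Appendix 9 and a clarification in section 12.5. The downside is that the investigators learn the active and placebo codes up to about three months later.

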APPENDIX 10: Participant Withdrawal

Parents have the right to withdraw their children, and children have a right to withdraw themselves, from the trial at any time for any reason, without their medical care being affected. Parents and children also have the right to decline to continue with any aspect of the research, without withdrawing and without their medical care being affected.

Data already collected will continue to be used in the trial and parents who withdraw their children from the trial will be asked if they are still willing to provide follow-up data via the Symptom and Recovery Questionnaire. Furthermore, we intend to conduct telephone interviews with parents who decide to withdraw (n=10). If a child is withdrawn, the reason for and type of withdrawal will be documented in the CRF. For example, type of withdrawal may include:

- 1. Trial use of baseline (CRF) data
- 2. Use of trial medication
- 3. Completing Symptom and Recovery Questionnaire
- 4. Receiving telephone calls, letters, email or texts to support Symptom and Recovery Questionnaire completion
- 5. Review of their primary care record
- 6. Completion of the postal Quality of Life (QoL) questionnaire at 3 months
- 7. Any combination or all of the above

The Principal Investigators also have the right to withdraw children from the trial drug in the event of inter-current illness, Adverse Events (AEs), Serious Adverse Events (SAEs), Suspected Unexpected Serious Adverse Reactions (SUSARs), protocol violations, administrative reasons or other reasons. The reason for withdrawal will be documented in the CRF. If the child is withdrawn due to an adverse event, the investigator will arrange for follow-up visits or telephone calls until the adverse event has resolved or stabilised. It is understood by all concerned that an excessive rate of withdrawals can render the trial un-interpretable, therefore unnecessary withdrawal of children will be avoided.

We will request return of the trial Medicine Packs from the parents of children who are withdrawn from the trial. Recruitment will continue until the required number of follow-up datasets are received, thereby replacing any children who have been withdrawn before Symptom and Recovery Questionnaire outcomes are collected.

A formal SOP will be developed to describe the process for declining to continue with elements of the research and for withdrawing from the trial.

